Composite endpoints have been used in pediatric intensive care studies with variable and limited success^{19 1}. Validity of these composite endpoints is often questioned. Frequently used endpoints such as time in intensive care unit and hospital stay are burdened by variable practice in a multi-center study. Additionally transfers require staff availability, which is not always feasible. For instance, some of the participating centers in the TRICC trial discharged patients to home directly from the intensive care unit. TTE is considered an important clinical endpoint and benchmark in pediatric cardiac surgical series. Mechanical ventilation is an important source of anxiety for parents with children in the intensive care unit²⁵. Furthermore, we successfully detected differences in TTE in TRICC, establishing that T3 supplementation affects this endpoint. Therefore TTE was selected as an objective outcome measure for this study. We recognize this endpoint has limitations, due to

ambiguity of start and stop time. First, time 0, the start of the intubation period, has been poorly defined in multiple analyses evaluating pediatric cardiac surgery. Start time has been defined as initial time to intubation prior to surgery, entrance into the operating room, or surgical completion. None of these time-points have relevance to surgical outcome, and are influenced by factors such as the complexity of the procedure and skill of the surgeon. Therefore, time from aortic cross-clamp removal will be defined as time 0 (start time) because under this definition it can be objectively measured.

In TRICC-2, all participating investigators will commit to reducing non-patient related delays in extubation and document the time of readiness to extubate along with any reason for delay, if a delay cannot be avoided. **For the calculation of the primary endpoint, the actual extubation time will be used.** It is essential that treating physicians are blinded to treatment assignment to prevent bias in deciding appropriate extubation time.

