hours from termination of cardiopulmonary bypass to readiness for ICU discharge. The intensivists and investigators agreed to record this endpoint (R-ICU) when both of the following parameters are reached: 1) all inotropic drugs terminated; 2) patient extubated and in no respiratory distress, only oxygen supplied by nasal cannula or mask; 3) If on high flow nasal cannula Max O₂ 4L (0-90d old) or 6L (91d-2y), FiO₂ ≤ 50%:

As noted previously, delayed TTE is a direct predictor of “oral feeding difficulty” resulting in hospital discharge on alternate feeding modes such as nasogastric tube^{23, 24}. Discharge with nasogastric tube reduces quality of life for infants and families. Therefore we will use **discharge on full oral feeds as a secondary quality of life end point**.

In order to assess cardiac endpoint parameters we will use **Low Cardiac Output Syndrome (LCOS) as another secondary endpoint**. This assessment will be completed on a separate CRF for LCOS for the first 36 hours after ICU admission and will include 1) identifying clinical signs/symptoms present in LCOS; 2) identifying all interventions involved in the treatment of LCOS; 3) Pharmacologic Assessment of inotropes/vasopressures

Summary of secondary endpoints

- 1) ICU-LOS
- 2) R-ICU
- 3) Discharge on Oral feeds
- 4) LCOS
- 5) Mortality*
- 6) Mortality and/or mechanical circulation (ECMO)*
 - *The PI anticipates that the study is inadequately powered to detect differences in these endpoints between treatment groups, but they were suggested by the FDA regulators.
- 7) Time to sternal closure for patients with delayed surgical closure

[figure not shown]

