6. 24 hours post 1st Triostat bolus
 - a. PK/thyroid hormone Blood Sample (±1hour)
 - b. Record I/O for previous 24 hours
 - c. Echo
7. 48 hours
 - a. Record I/O for previous 24 hours
 - b. Stop Triostat infusion (either here or at extubation, whichever is sooner)
8. 72 hours post 1st Triostat bolus
 - a. PK/thyroid hormone Blood Sample (±1hour)
 - b. Record I/O for previous 24 hours
 - c. Echo
9. 30 day follow-up (Chart Review – to be completed 30 days post stoppage of medication)
 - a. AE assessment
 - b. Vital Status
 - c. Feeding Status
10. Endpoints: Date and time to be recorded for the following (if applicable)
 - a. Primary
 - i. Extubation
 - b. Secondary
 - i. ICU discharge/ready for ICU discharge
 - ii. Feeding tube stop time
 - iii. Time of sternal closure
 - iv. Death (if applicable)
 - v. ECMO start (if applicable)

11. Timepoints to be recorded

- a. Aortic Cross Clamp time
- b. Release of Aortic Cross Clamp time
- c. ICU discharge time/ready for ICU discharge time
- d. Feeding tube stop time
- e. Time of sternal closure
- f. Death (if applicable)
- g. ECMO start (if applicable)

- The aortic cross clamp removal time used should be the first instance of cross clamp removal. The cross clamp may be removed and reclamped, however the schedule of events is timed off of the first cross clamp removal time.
- Blood draw windows apply only if there are vascular lines in place that can be drawn from. In the event that lines have been discontinued, it is acceptable to have study samples drawn at the time of the closest clinical draw (non study-driven blood draw) to a timepoint. Missing or late blood draws due to a lack of a vascular line or no timely clinical blood draws will not be considered a deviation. This most likely applies to the 72 hour blood draw timepoint.
- The medication bolus and infusion will be given in the 1 hour window after cross clamp removal.
- The medication infusion will be stopped in a ± 2 hour window after either extubation or 48 hours after cross clamp removal, which ever comes first.
- Concomitant medications include medications taken in the 4 weeks prior to hospitalization and continue through 30 day follow-up discharge of the index hospitalization.
- Capture of hemodynamic parameters & lactate levels will be captured as part of standard of care measurements and will not be driven by the protocol. Hemodynamic parameters will be captured for the duration of the study

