Thus, patients randomized but not receiving study medication will not be included in the analysis. Counting patients who receive at least 1 dose of study drug will improve the scientific validity of the study, and reduce the overall cost and duration of this trial. Patients who receive at least 1 dose will be analyzed according to randomization assignment regardless of the treatment actually received. The TTE distributions will be compared across treatment groups using the Log-Rank test. Time zero will be defined as the time of cross-clamp removal, and span until to the first of death, extubation or 21 days. Patients who die will be censored at the earliest of 21 days or death, and patients who are still intubated at 21 days post-cross clamp removal will be censored at 21 days. Medians and 95% confidence intervals for TTE will be based on the Kaplan-Meier estimate to account for censoring. A sensitivity analysis adjusting for non-patient-related delays will also be performed to determine the impact of these delays, which we expect to be few, on the primary efficacy analysis. Differences in death will be compared using Fisher's Exact Test.

Secondary endpoints as previously described will be analyzed using similar methodology. Endpoints with censored observations will be addressed using survival analysis techniques to account for censoring.

This study is powered to detect a hazard ratio of 1.8 with respect to TTE in patients less than 4 weeks of age (assuming half of the total sample is in this age range). The effect in patients < 4 weeks of age is an important clinical outcome as these are the sickest patients in the population, and reduction in their relatively long intubation times provides more opportunity for benefit. There will be no Type I error adjustment for this subgroup analysis in order to maximize power for the primary outcome, but the sample size was determined considering the need to report the effect in the youngest patients. Thus, this analysis will be considered supportive and will be described as such in subsequent publications.

Patient characteristics and adverse events will be compared using the chi-square test or Fisher's Exact test as appropriate. Continuous characteristics and outcomes will be compared using the T-test or ANOVA for repeated measures. Point estimates for hazard ratios and 95% (2-sided) confidence intervals will be reported.

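### The ready-for-ICU-discharge clock can start after study drug has begun; starting it at first cross-clamp removal would align it with time to extubation at little cost

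*Combined protocol and SAP*

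**What the plan says.** Secondary Endpoints defines R-ICU as "hours from termination of cardiopulmonary bypass to readiness for ICU discharge". The endpoint is recorded "when both of the following parameters are reached", after which three numbered items follow: inotropes stopped, extubated without respiratory distress, and limits that apply if the infant is on high-flow cannula.

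The primary endpoint uses a different start. Primary Clinical Endpoint says that "time from aortic cross-clamp removal will be defined as time 0 (start time) because under this definition it can be objectively measured", and Statistical Analysis repeats it: "Time zero will be defined as the time of cross-clamp removal, and span until to the first of death, extubation or 21 days". For the other endpoints that section says only "Secondary endpoints as previously described will be analyzed using similar methodology" and does not restate a time origin for R-ICU.

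The notes to the Schedule of Events fix the timing of treatment: "The medication bolus and infusion will be given in the 1 hour window after cross clamp removal". They add that "The aortic cross clamp removal time used should be the first instance of cross clamp removal", even if the aorta is clamped again. Item 11 of the schedule lists "Release of Aortic Cross Clamp time" among the timepoints to record. End of bypass is not in that list. For infants who are not cross-clamped, Triostat Dosing and Blinding and Randomization refer to a surrogate time point, which is not defined.

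**The concern.** In a randomised comparison the clock should start no later than treatment. Clamp removal meets that condition here, because dosing follows it. End of bypass need not, because nothing in the schedule makes dosing wait for it. Two consequences follow.

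- **Origin after treatment.** The Significance section reports that T3 improved echocardiographic function in TRICC. If better function also changed how quickly infants come off bypass, the start of the R-ICU clock would move with treatment, and time gained or lost in weaning would fall outside the endpoint.
- **Undefined origin.** The analysis set is every randomised infant who received at least one dose. A dosed infant who never separates from bypass belongs to that set but has no R-ICU start time.

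The cited neonatal infusion study began drug directly after bypass ended (Triostat Dosing), so a bypass-end clock could not follow treatment there. That ordering does not carry over to this trial.

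At stake is the clean reading of an endpoint introduced because ICU stay is affected by matters such as step-down unit availability.

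**Working it through.** **1. Order of events in the documents**

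| Event | Timing | Section |
|---|---|---|
| First clamp removal | Time 0 for TTE | Primary Clinical Endpoint; Statistical Analysis |
| Bolus and infusion | Within 1 h after clamp removal | Schedule of Events, notes |
| End of bypass | Starts R-ICU; no interval given | Secondary Endpoints |

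Drug can precede end of bypass. How often it does cannot be derived from the documents.

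**2. The plan's own figure.** None is given for R-ICU. The only sizing statement concerns TTE: more than 80% power with 220 enrolled, hazard ratio 1.55, two-sided 0.05, 1:1. Schoenfeld's formula gives 4 × (1.960 + 0.842)² / (ln 1.55)² ≈ 164 events for 80% power; 220 events would give 90.2%. The statement reproduces as a bound and does not depend on the R-ICU clock.

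**3. Size of the omitted interval.** Let g be the time from clamp removal to end of bypass. Then R-ICU from clamp removal = R-ICU from end of bypass + g. Assume g = 0.5 to 2 h. As a proxy for R-ICU, take the TRICC median ICU stays in Secondary Endpoints:

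- 4 weeks or younger: 7.5 d (180 h) with T3, 8.5 d (204 h) with placebo; difference 24 h.
- Older than 4 weeks: 4.5 d (108 h) with T3, 7 d (168 h) with placebo; difference 60 h.

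Smallest share: 0.5/204 = 0.2%. Largest share: 2/108 = 1.9%. R-ICU should be shorter than ICU stay, so these shares may be somewhat low. Since R-ICU requires extubation, the TRICC T3-arm median TTE of 55 h under 5 months (Significance) is a harsher yardstick: 2/55 = 3.6%.

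**4. If the drug shifts end of bypass.** Suppose T3 shortens g by d = 0.25 to 1 h (assumed). The bypass-end clock then understates the T3 benefit by d:

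- 4 weeks or younger: 0.25/24 = 1.0% to 1/24 = 4.2% of the difference.
- Older than 4 weeks: 0.25/60 = 0.4% to 1/60 = 1.7% of the difference.

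**5. Effect on the hazard ratio.** A Cox model was fitted to simulated log-normal times with the medians above (log-SD 0.7 assumed, 20,000 per arm, censored at 21 days).

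| Age group | Clamp origin | Bypass-end origin, g = 1 h in both arms | Bypass-end origin, g = 2 h placebo, 1 h T3 |
|---|---|---|---|
| 4 weeks or younger | 1.179 | 1.179 | 1.172 |
| Older than 4 weeks | 1.761 | 1.760 | 1.747 |

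An equal gap in both arms changes almost nothing. A 1 h drug-induced shift lowers the hazard ratio by about 0.01, toward no effect.

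**The case against.** The case for leaving the definition alone is strong on size. No section gives the clamp-to-bypass-end interval or reports a drug effect on weaning, and every calculation above rests on assumed gaps. End of bypass occurs in almost every infant, because bypass is an inclusion criterion, whereas some infants have no clamp and would need a surrogate that is not yet defined. R-ICU is also modelled on an earlier pilot composite, so a new origin costs some comparability. All of this stands. It makes the point minor, but it does not remove the post-dose origin or the missing start time.

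Several stronger readings are tempting and are not supported:

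- **The arms have different clocks, so the comparison is not randomised.** One definition applies to both blinded arms. A material distortion would need a drug-driven shift or a loss of patients, and the documents show neither.
- **Infants moved to ECMO have that time removed.** Nothing in the definition treats ECMO as continued bypass. Read plainly, bypass ends at the changeover, the clock starts, and later ECMO time counts.
- **End of bypass is not collected.** Item 11 of the schedule is not exhaustive. It also omits extubation, which appears in item 10, and the protocol says that further data are captured on accompanying forms.
- **The sponsor has already rejected end of bypass as a start.** The starts rejected for TTE are initial intubation, entry to the operating room and surgical completion. The remark about complexity and surgeon skill applies to end of bypass only by analogy.
- **The stop rule is seriously ambiguous.** The third item is conditional and reads naturally as a limit on the second. The mismatch between the wording and three items is a drafting slip.

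**Conclusion.** The concern holds as a minor misalignment in one of seven secondary endpoints. The documents establish that the R-ICU clock can start after the first dose and that it has no defined start for a dosed infant who never separates from bypass. The number of such infants cannot be derived. That treatment moves the end of bypass is only a possibility.

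Under assumed gaps of 0.5 to 2 h, the omitted time is about 0.2% to 1.9% of the TRICC median ICU stays, which stand in for R-ICU. An assumed 1 h shift changes the hazard ratio by about 0.01, and if T3 speeds weaning, the error understates benefit. The primary endpoint, its power and the sample size are unaffected.

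**What to change.** Define R-ICU as hours from first aortic cross-clamp removal, the same time zero as TTE, to the first time that all applicable listed criteria hold. Replace the word both accordingly. State in Statistical Analysis that R-ICU uses this origin.

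For infants without a clamp, use the surrogate time point on which the trial already relies for dosing and sampling, and specify it before unblinding. TTE needs the same specification, because its time zero is also clamp removal.

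The cost is small. Clamp-release time is already on the list to record, and no sample size changes. What remains is the work of specifying the surrogate and slightly less comparability with the pilot composite. If end-of-bypass times are captured, the current definition can be reported as a sensitivity analysis to preserve that link.

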The primary analysis will be performed using Cox Proportional Hazards, including terms for stratification factors, and delayed sternal closure. Patients will be included in analyses if they were randomized and received at least one dose of study drug according to the principal of Intention-to-Treat (ITT). Occasionally patients are randomized and then surgery is cancelled or rescheduled due to scheduling conflicts, and not due to patient related issues. This can rarely result in the patient missing the study medication when the operation is rescheduled at the last minute. However, since this study is double-blind, the ITT principal is preserved because the treatment assignment is blinded and so unknown to persons responsible for these decisions.

As stated in ICH-E9, Statistical Principles for Clinical Trials posted on the FDA website: "Subjects who fail to satisfy an entry criterion may be excluded from the analysis without the possibility of introducing bias only under the following circumstances: In some situations, it may be reasonable to eliminate from the set of all randomized subjects any subject who took no trial medication. The intention-to-treat principle would be preserved despite the exclusion of these patients provided, for example, that the decision of whether or not to begin treatment could not be influenced by knowledge of the assigned treatment."

<http://www.fda.gov/downloads/Drugs/GuidanceComplianceRegulatoryInformation/Guidances/UCM073137.pdf>

Thus, patients randomized but not receiving study medication will not be included in the analysis. Counting patients who receive at least 1 dose of study drug will improve the scientific validity of the study, and reduce the overall cost and duration of this trial. Patients who receive at least 1 dose will be analyzed according to randomization assignment regardless of the treatment actually received. The TTE distributions will be compared across treatment groups using the Log-Rank test. Time zero will be defined as the time of cross-clamp removal, and span until to the first of death, extubation or 21 days. Patients who die will be censored at the earliest of 21 days or death, and patients who are still intubated at 21 days post-cross clamp removal will be censored at 21 days. Medians and 95% confidence intervals for TTE will be based on the Kaplan-Meier estimate to account for censoring. A sensitivity analysis adjusting for non-patient-related delays will also be performed to determine the impact of these delays, which we expect to be few, on the primary efficacy analysis. Differences in death will be compared using Fisher's Exact Test.

Secondary endpoints as previously described will be analyzed using similar methodology. Endpoints with censored observations will be addressed using survival analysis techniques to account for censoring.

This study is powered to detect a hazard ratio of 1.8 with respect to TTE in patients less than 4 weeks of age (assuming half of the total sample is in this age range). The effect in patients < 4 weeks of age is an important clinical outcome as these are the sickest patients in the population, and reduction in their relatively long intubation times provides more opportunity for benefit. There will be no Type I error adjustment for this subgroup analysis in order to maximize power for the primary outcome, but the sample size was determined considering the need to report the effect in the youngest patients. Thus, this analysis will be considered supportive and will be described as such in subsequent publications.

Patient characteristics and adverse events will be compared using the chi-square test or Fisher's Exact test as appropriate. Continuous characteristics and outcomes will be compared using the T-test or ANOVA for repeated measures. Point estimates for hazard ratios and 95% (2-sided) confidence intervals will be reported.

Safety endpoints include arrhythmias, infection rate, serious, and non-serious adverse events. Only treatment-emergent events with signs or symptoms that begin or worsen after the first dose of study drug will be reported.

Total T3 levels will be analyzed to determine half-time using a single compartmental pharmacokinetic model similar to previously published methodology by the PI ²⁹.

Safety

Adverse Event (AE) Reporting

Reporting of adverse events in cardiac surgical trials in infants is complicated as there is no regulatory guidance specific to conducting clinical research in critically ill children. The Pediatric Heart Network reported a new method of reporting using predefined "sentinel events" in place of serious adverse events (SAEs). All other adverse events were reported as "complications". The standard definitions using "Common Terminology Criteria for Adverse Events" (CTCAE), developed by the National Cancer Institute does not carry enough appropriate pediatric codes to cover the complexity of the postsurgical population. The Pediatric Heart Network (PHN) launched the Single Ventricle Reconstruction Trial and midway switched from standard reporting to their new system identifying "sentinel events"^{30, 31}. This system reduced administrative burden and improved quality of safety reporting. However, their study which evaluated surgical techniques against one another was not performed under IND and according to PHN investigators their system has not been reviewed by the FDA. On query regarding the appropriateness for using the PHN published method for reporting adverse events in a drug trial the FDA responded: *"Our goal is to understand the effect of said study treatment on adverse events, i.e., "adverse reactions" (to study drug), not to catalog all bad things that happen to subjects. In this respect, the process PHN followed may or may not be reasonable. One would need to think through whether the experimental treatment had any likelihood of affecting the common adverse events associated with surgery and whether the investigators were likely to be able to distinguish study treatment-related events from "normal" (clinically expected) ones."*

As TRICC-2 will be performed with IND requirements, we will need to report adverse events (AEs) using FDA standards revised by the common rule amendments of 21 CFR Parts 312 and 320 (April 2011). The common rule does reduce reporting requirements somewhat as long as expected AEs and SAEs are predefined in the study protocol (see Appendix 1). A summary of adverse events reported for the TRICC trial appears in Table 3. This shows that the majority of patients show AEs, though relatively few have SAEs using standard reporting methodology. Thus, the greatest burden for reporting may not be related to SAEs but to reporting of common procedural complications as AEs regardless of severity. Using literature review and expert consensus, the PHN developed lists defining common and specific AEs which occur in this infant population undergoing cardiac surgery. Protection of Human Subjects (section 6) contains a list adapted from the PHN,

which defines expected surgical complications or AEs. For instance pleural effusion is defined as an adverse event when drainage exceeds 7 days after surgery. This definition will reduce reporting of pleural effusions. In an effort to address the issue raised by the FDA with regard to affect on common adverse events in this population, we have numerically coded the complication table generated by the PHN (section 6).

Summary of Adverse Events from Time of Surgery to the First of Hospital Discharge, 30 Days Post-procedure or Death for entire cohort and < 5 months						
	Placebo Total (N=95)	Triostat Total (N=98)	P	Placebo, < 5 months (N=50)	Triostat, < 5 months (N=48)	P
At Least One AE	82 (86.3%)	80 (81.6%)	0.376	45 (90.0%)	42 (87.5%)	0.695
At Least One Serious AE	12 (12.6%)	14 (14.3%)	0.736	8 (16.0%)	8 (16.7%)	0.929
At Least One Unexpected AE	40 (42.1%)	40 (40.8%)	0.856	25 (50.0%)	22 (45.8%)	0.68
At Least One Possibly Treatment-Related AE	45 (47.4%)	57 (58.2%)	0.151	26 (52.0%)	34 (70.8%)	0.065
Death (any time on study)	5 (5.3%)	3 (3.1%)	0.493	4 (8.0%)	3 (6.3%)	1
Death or Mechanical Life Support	5 (5.3%)	3 (3.1%)	0.493	4 (8.0%)	3 (6.3%)	1
Arrhythmia AE	9 (9.5%)	11 (11.2%)	0.69	7 (14.0%)	7 (14.6%)	0.934
JET	7 (7.4%)	8 (8.2%)	0.837	5 (10.0%)	5 (10.4%)	0.946
SVT	2 (2.1%)	3 (3.1%)	1	2 (4.0%)	2 (4.2%)	1
VT	1 (1.1%)	0 (0.0%)	0.492	1 (2.0%)	0 (0.0%)	1

Table 3. TRICC data. Table shows no significant difference in rates of adverse events between placebo and Triostat groups. Postoperative arrhythmias served as an index safety factor.

Compliance and Monitoring

IND # 55367 has been assigned by the FDA, which has instructed the PI that amendment and modification only is needed for performance of TRICC-2, rather than new IND. IND amendment was submitted on December 8. We will subcontract with an independent clinical research organization (CRO) to perform monitoring for our study. The CRO, Clinical Research Staff Support Core (CRSSC), has considerable experience in monitoring the conduct of clinical trials in children. The TRICC-2 study will be performed under the Guidelines of Good Clinical Practices as outlined in FDA document "Guidance for Industry E6 Good Clinical Practice: Consolidated Guidance".

We will list the study on ClinicalTrials.gov. [name] as PI and holder of the IND will serve as sponsor. Division of responsibilities between the PI and the CRO are included in the table below. The PI will be supported by experienced study personnel at the Seattle Site. X = responsible; NR –not responsible, SIV – site initiation visit, IMV, interim monitoring visit, COV- close out visit.

Table 4. Division of Interim Monitoring Duties between Sponsor ([name]) and Clinical Research Organization (CRSSC).

Monitoring	PI	CRO
1. Qualify sites	X	NR
2. Provide Monitoring services (SIV, IMV, COV) at US sites; 200 patients; First IMV after enrollment of 2 patients; subsequent visits after enrollment of 5 patients at each site.	NR	X
3. Provide monitoring reports and follow up letters to sites after each visit	NR	X
4. Final review and approval of monitoring reports	NR	X
5. Conduct drug accountability at site during IMVs (see below)	NR	X
6. Review SAEs during IMVs	NR	X
Regulatory		
1. Collect required essential documents including CRFs from each site	NR	X
2. Review and approve essential documents	NR	X
3. Provide essential regulatory documents (e.g. CV of PI, FDA1572 Form, IRB approval) to [name] for submission to regulatory agency (FDA)	NR	X
4. Submit essential documents to regulatory agency	X	NR
5. Track regulatory documents for all sites	NR	X
6. Assist sites with regulatory submission to IRBs	NR	X
7. Submit SAEs to regulatory agency	X	NR
8. Prepare IND safety reports for submission to sites, DMC, and regulatory agency	X	NR
9. Track IND safety reports	x	NR

Monitors will be blinded. **Therefore, they cannot perform on-site drug accountability monitoring. This task will be performed by the Seattle Children’s Investigational Drug Service pharmacist for all sites.**

Data Management

Seattle Children’s Hospital and Research Institute will serve as the central site and data repository. The CRO will oversee completion of clinical research forms (CRFs) and transfer original CRFs to SCH for input into the central data base. [name] staff will generate final queries to each site. The Research Electronic Data Capture (REDCap) database created at Vanderbilt University will be used as the study database. We will use a double entry to avoid input errors. Data will be stripped of identifiers (according to HIPAA) prior to transfer. Each patient will be assigned a study number with code to identifiers kept securely at each individual site. The database will undergo intermittent internal audit to ascertain that CRF data are correctly inputted. The auditor, not yet assigned, will be a different individual than Database manager.

Data Monitoring Committee

The DMC will be an independent multidisciplinary group consisting of clinicians with collective experience in the management of infants after cardiopulmonary bypass and in the conduct and monitoring of clinical trials. DMC members will be pediatric cardiologists, pediatric cardiac surgeons and/or pediatric cardiac intensivists, and a bioethicist. A biostatistician will also serve on the DMC to advise the committee on the interpretation of statistical data provided by the independent statistician. Members will be appointed by the DMC Chair in consultation with [name]. Blinded and unblinded data reports will be produced by an independent statistician at Axio Research. This statistician will be available to present unblinded analyses in the closed sessions of the DMC meeting. The DMC will ratify a charter at their first meeting.

